DLBCL	Diffuse Large B-cell Lymphoma
ECG	Electrocardiogram
EOT	End of Treatment
FFPE	Formalin-Fixed Paraffin-Embedded
GCB	Germinal Center B-Cell

Abbreviation or Specialist Term	Definition
GCP	Good Clinical Practice
IB	Investigator's Brochure
ICH	International Council for Harmonization
IRB	Institutional Review Board
IWCLL	International Workshop on Chronic Lymphocytic Leukemia
LDH	Lactate Dehydrogenase
MAD	Multiple Ascending Dose
MCL	Mantle Cell Lymphoma
MRD	Minimal Residual Disease
MTD	Maximum Tolerated Dose
NGS	Next-generation sequencing
ORR	Overall Response Rate
OS	Overall Survival
PD	Progressive Disease
PFS	Progression Free Survival
РК	Pharmacokinetics
РКС	Protein Kinase C
PLCG2	Phospholipase C gamma 2
PR	Partial Response
PRwL	Partial Response with lymphocytosis
QD	Quaque die/ once a day
QTCF	QT interval, corrected by Fridericia method
RP2D	Recommended Phase 2 Dose
SAD	Single Ascending Dose
SAE	Serious Adverse Event
SD	Stable Disease
SLL	Small lymphocytic lymphoma

Abbreviation or Specialist Term	Definition
SRC	Safety Review Committee
ТВО	To be determined
TEAE	Treatment Emergent Adverse Event
TLS	Tumor Lysis Syndrome
ТР53	Tumor Protein P53
T _{max}	Time to reach maximum (peak) concentration of drug
t _{1/2}	Terminal half-life
WBC	White Blood cells
WHO	World Health Organization

1. INTRODUCTION

1.1. Chronic Lymphocytic Leukemia

Chronic lymphocytic leukemia (CLL) is the most common leukemia in United States adults, accounting for about one third of all new cases of leukemia as well as one third of all leukemia deaths.¹ CLL as a cancer is defined by an excess of clonal, abnormal B lymphocytes, accumulation of which was historically believed to be solely (at least in early stage disease) due to evasion of apoptosis, although we now know that that there is a significant proliferative component to CLL^{2,3} frequently in the protective and nurturing microenvironment of hematopoietic tissues, such as the bone marrow and lymph node.

Traditionally, therapy for CLL has consisted of a sequence or combination of cytotoxic chemotherapy and monoclonal antibody immunotherapy. Response rates for front line chemoimmunotherapy therapy are good, and can exceed 90%, but relapse is inevitable and CLL is therefore currently considered an incurable disease. Patients who relapse after initial chemoimmunotherapy at present have limited treatment options outside the context of a clinical trial, and responses to agents in second line and beyond are often fair at best. Furthermore, the molecular biology—and hence the clinical course— varies significantly among patients, and of patients with poor-risk genetic features no currently approved therapies seem to produce durable and robust responses. With a view to improve response rates and response durability among all patients, including high-risk patients, and with an increased understanding of the mechanisms of CLL, recent clinical work has shifted toward targeted therapy with small molecules and engineered antibodies: there have been a number of successes in targeting key points in B-cell receptor (BCR) signaling and the NF-κB cascade, as well as various cell-surface markers, especially CD20.

1.1.1. B Cell Receptor (BCR) Signaling Inhibitors

Because activated BCR signaling seems to be a *sine qua non* of CLL, much work has been devoted to targeting components of this pathway. The BCR complex itself is a transmembrane immunoglobulin molecule partnered with a CD79 heterodimer. Ligation of the BCR results in phosphorylation of an intracytoplasmic domain of CD79, which then signals through multiple pathways, notably through BTK (Bruton's Tyrosine Kinase), PLCG2, and PI3K. Upregulation of genes involved in these pathways has been observed in CLL and represent targets.⁴ In fact, targeting BTK as a component of the BCR pathway has shown enormous promise in multiple clinical trials and has led to FDA approval of the first-in-class BTK in both the upfront and relapsed setting. ^{5,6}

However, because of tumor heterogeneity, genomic instability, and historic experience with other targeted agents, it is not surprising that CLL would develop resistance mutations in response to prolonged monotherapy with a BTK inhibitor. A recent report of 3 patients who had progressed on ibrutinib utilized next-generation sequencing techniques to look for mutations arising from exposure to the BTK inhibitor.⁷ Investigators discovered two mutations in BTK and one constitutive gain-of-function mutation in PLCG2, a substrate of BTK. We have subsequently identified additional mutations in PLCG2 among ibrutinib-treated patients.

1.1.2. Protein Kinase C and PKC-β

Immediately downstream of PLCG2 lies Protein Kinase C beta (PKC- β), at the confluence of the BCR pathway, the NF- κ B cascade, and the RAS/RAF/MEK/ERK pathway; PKC- β is thus a critical downstream effector in BCR signaling. In healthy B lymphocytes, PKC- β is important in the transduction of normal BCR signals. However, it has been well-demonstrated that constitutive activation of BCR signaling plays a key role in the maintenance of the CLL cell,⁸ and as a consequence of this it stands to reason that PKC- β therefore occupies a position of both considerable import and opportunity. By acting immediately downstream of the BTK and PI3K components of the BCR signaling pathway, modulation of PKC- β has the potential to bypass mechanisms of resistance effected by mutations in these genes, and targeting PKC- β in this patient population is a rational and highly promising strategy.

PKC-β, encoded by the gene *PRKCB*, is a member of a large family of protein kinases responsible for phosphorylation of serine and threonine residues of downstream effector proteins; PKC-β is, like the other two other members of the "conventional" protein kinase C subfamily PKC-α and PKC-γ, activated by the second messengers diacylglycerol and Ca²⁺, whereas members of the novel subfamily (PKC delta, eta, epsilon, and theta) require only diacylglycerol.⁹ While PKC family proteins are present across many cell types, normal and malignant B lymphocytes express only a few of these at a significant level, including PKC-β and PKC-δ. PKC-β is exceptional among the others, however, for being much more highly expressed in CLL cells compared to normal B cells: *PRKC-*6 mRNA transcripts are up to 8 fold higher in some CLL cells than in normal B cells in our unpublished observations, and others have shown that the protein product exists as a higher proportion of total cellular protein compared to normal B cells. ¹⁰ This is likely reflective of the combination of high levels of BCR signaling in CLL compared to normal B cells and the critically of PKC-β within this network. Not surprisingly, the previously mentioned study and others have shown that *in vitro* inhibition of PKC-β has a detrimental effect on CLL cell

survival. ¹⁰⁻¹² Indeed, *TCL1tg*, PKC- β null mice even failed to develop leukemia. ¹³ Other forms of PKC likely also play a part in the signal transduction that sustains CLL: the delta form of PKC (PKC- δ) has also been shown to interact with PI3K in CLL cells and inhibition of PKC- δ enhanced apoptosis of CLL cells, but not normal B cells. ¹⁴

1.1.3. PKC in the Microenvironment

PKC inhibition appears to have relevance beyond the tumor cell itself, extending also into the microenvironment. Experiments with *Prkcb* knockout mice demonstrated the importance of PKC- β and subsequent NF- κ B signaling in the microenvironment: CLL-like leukemia cells from *TCL1tg* mice would not engraft in *Prkcb-/- mice* whereas wild-type mice succumbed to disease. ¹⁵

The possibility that systemic inhibition of PKC even in non-tumor tissues could provide additional benefit thus provides further rationale for the use of PKC inhibitor in CLL. Separate from this, we have found that the PKC inhibitor sotrastaurin also activates GSK- β via dephosphorylation in the 2-5 μ M range with subsequent decrease in B-catenin levels with concomitant decrease in Myc, Cyclin D1, and Mcl-1 expression. Given that previous studies have demonstrated that the WNT/ β - catenin levels are active in CLL and also have frequent

mutations, pursuing PKC inhibitors as therapeutic agents targeting WNT is worthwhile and may provide a pharmacodynamic endpoint to study the effect of this therapy in vivo.

1.1.4. Autoimmunity

Besides the role of PKC-ß in transducing the overactive BCR signals in CLL cells, the PKC family of kinases has been shown to be crucial to the regulation and normal function of both normal T cell and B cell lymphocytes, and their contribution to autoimmune diseases. The three isoforms, PKC- θ , PKC- α and PKC- β , appear to be most important for lymphocyte function. PKC- θ is downstream of the T cell receptor complex and is required for effector T cell activation, function, survival, and autoimmune stimulation. Interestingly, PKC- θ negatively regulates the function of regulatory T cells and therefore inhibition of PKC- θ enhances the function of regulatory T cells. PKC- α plays a non- redundant role and collaborates with PKC θ in T effector cell activation and function. As in CLL, PKC- β plays a key role in B cell activation, function, survival, and the dysfunction seen in autoimmunity.

Interestingly, inhibition of PKC- δ , in contrast to other isoforms, appears to have the potential to induce autoimmune disease in B cells. Previous PKC inhibiting compounds (e.g., enzastaurin, sotrastaurin) inhibit PKC- δ as well as PKC- β . MS-553, a novel PKC- β inhibitor lacks PKC- δ inhibition while selectively inhibiting PKC- β and to slightly lesser extent PKC- α and PKC- θ . These features of MS-553 effectively combine to downregulate autoimmune stimulation of B and T cells while enhancing the function of regulatory T cells. Avoidance of autoimmunity is key, because complications related to enhanced T cell function including fatal pneumonitis and colitis have been reported with other kinase inhibitors in CLL and lymphoma.

1.2. MS-553

MS-553 (chemical name: ((2S,5R)-2,5-dimethyl-4-((tetrahydro-2H-pyran-4- yl)methyl)piperazin-1-yl)(3-(5-fluoro-2-methylpyrimidin-4-ylamino)-6,6-dimethylpyrrolo[3,4-c]pyrazol-5(1H,4H,6H)yl)methanone) is a selective inhibitor of PKC activity. It has a molecular weight of 500.6 g/mol and is orally bioavailable in humans. For clinical testing it can be formulated with high purity to GMP standards. MS-553 is an investigational product and has not been approved for marketing in any country.

1.2.1. Mechanism of Action

[figure not shown]
Nonclinical pharmacology studies have demonstrated that MS-553 is a potent, ATPcompetitive and reversible inhibitor of several classical PKC enzyme isoforms with a Ki =5.3 nM for recombinant PKC- β and a Ki = 10.4 nM for recombinant PKC- α . It also is a potent inhibitor of the novel isoform PKC- θ with an IC50 = 25.6 nM. MS-553 does not inhibit PKC- δ (IC50 > 1000 nM). Additionally, screening a broad panel of protein kinases reveals that MS-553 is very selective against kinases other than PKC.

MS-553 has been shown to be efficacious in several cell lines and a xenograft model of diffuse large B cell lymphoma that are driven by chronic activation of BCR-NFkB signaling due to CD79 mutation. In addition, several nonclinical studies also demonstrated that MS-553 is effective in

autoimmune disease models of lupus, rheumatoid arthritis, multiple sclerosis, and uveitis. For more information on the pharmacology see the MS-553 Investigator's Brochure (IB).

1.2.2. Safety Pharmacology

A core battery of safety studies performed in nonhuman animals (rat; dog) indicated no undesirable pharmacodynamics effects of MS-553 on physiological functions in relation to exposure in the therapeutic range and above. No functional changes in vital organs or systems which are likely to be of importance in clinical testing of MS-553 were identified.

[figure not shown]
1.2.4. Summary of Clinical Experience with MS-553

MS-553 has been explored in single ascending dose (SAD) (protocol 2014-04-001) and multiple ascending dose (MAD) (protocol MS-553-102) studies in healthy human volunteers. MS-553 has not been studied in patients with cancer or other immune system diseases.

The Phase 1 SAD study evaluated doses ranging from 25 mg to 400 mg. Pharmacokinetic (PK) data from this study demonstrated that MS-553 was rapidly absorbed into systemic circulation with a T_{max} of 2-4 hours and was rapidly eliminated with a mean apparent terminal half-life (t ½)

of 10-14 hours. The t $\frac{1}{2}$ did not appear to be dose dependent. The inter-subject variability in exposure measures (C_{max} and AUC) and the t $\frac{1}{2}$ appears to be low. Increases in dosage led to mostly dose proportional increases in exposure. The PK behavior of MS-553 was similar when administered in either a fed or a fasted condition. While food did not change the PK profile of MS-553, gastrointestinal side effects decreased substantially when MS-553 is taken with food, as demonstrated in the MAD study.

In the SAD study, MS-553 was well tolerated; AEs were either mild or moderate and were observed predominantly in the highest active dose group (400 mg). The most frequently observed adverse events were nausea (9 subjects, 19% of subjects who received active drug), vomiting (4 subjects, 8% of subjects who received active drug), visual disturbance (4 subjects, 8% of subjects who received active drug), dizziness/vertigo (4 subjects, 8% of subjects who received active drug). All AEs were transient and resolved. Refer to the IB for additional details.

In the MAD study, MS-553 was well tolerated and all AEs were either moderate or mild. The most frequent observed AEs were headache (9 subjects, 37.5% of subjects receiving active drug), nausea (3 subjects, 12.5% of subjects receiving active drug), visual disturbance (3 subjects, 12.5% of subjects receiving active drug), neck pain (3 subjects, 12.5% of subjects receiving active drug), abdominal pain (3 subjects, 12.5% of subjects receiving active drug) and dizziness (2 subjects, 8.3% of subjects receiving active drug). All AEs were transient and resolved. Refer to the IB for additional details.

2. OBJECTIVES AND ENDPOINTS

2.1. Cohort A Objectives

2.1.1. Primary Objective

The primary objective of Cohort A is to:

- Evaluate the safety of MS-553 monotherapy in patients with CLL/SLL whose disease relapsed after or was refractory to at least two prior lines of therapies with the following exceptions:
 - Patients with a 17p deletion who have already received venetoclax, or
 - Patients who have *TP53* mutation (prior therapy is not required for these patients), or
 - Patients who have either acquired clinical and/ or molecular (e.g., BTK or PLCG2 mutation) resistance to a BTK inhibitor.
- Determine the MTD or the initial RP2D of MS-553 monotherapy.

2.1.2. Secondary Objective

[figure not shown]
The secondary objective of Cohort A is to:

- Evaluate the clinical activity of MS-553 in patients with relapsed or refractory CLL/SLL who
 - Have failed at least two prior lines of therapies, or
 - Have either acquired clinical and/ or molecular (e.g., BTK or PLCG2 mutation) resistance to a BTK inhibitor.
- Evaluate pharmacokinetics in patients receiving MS-553.

Pursuit of the secondary objective should not jeopardize the primary objective, which is safety.

2.1.3. Exploratory Objectives

Exploratory objectives of Cohort A include the following:

•

2.2. Cohort B Objectives

2.2.1. Primary Objective

The primary objective of Cohort B is to:

- Evaluate the safety of MS-553 in combination with acalabrutinib in patients with CLL/SLL.
- Determine the MTD or the initial RP2D of MS-553 in combination with acalabrutinib.

2.2.2. Secondary Objectives

The secondary objectives of Cohort B are to:

- Evaluate the clinical activity of MS-553 in combination with acalabrutinib in patients with CLL/SLL.
- Evaluate pharmacokinetics in patients receiving MS-553 in combination with acalabrutinib.

Pursuit of the secondary objectives should not jeopardize the primary objective, which is safety.

2.2.3. Exploratory Objectives

Exploratory objectives of Cohort B include the following:

2.3. Cohort C Objectives

2.3.1. Primary Objective

The primary objectives of Cohort C are to:

- Evaluate the safety of MS-553 in combination with venetoclax and rituximab in patients with CLL/SLL.
- Determine the MTD or the initial RP2D of MS-553 in combination with venetoclax and rituximab.

2.3.2. Secondary Objectives

The secondary objectives of Cohort C are to:

- Evaluate the clinical activity of MS-553 in combination with venetoclax and rituximab in patients with CLL/SLL.
- Evaluate pharmacokinetics in patients receiving MS-553 in combination with venetoclax and rituximab.

Pursuit of the secondary objectives should not jeopardize the primary objective, which is safety.

2.3.3. Exploratory Objectives

Exploratory objectives of Cohort C include the following:

2.4. Primary Endpoints

The primary endpoints of this study include:

- Safety
 - The incidence rate of dose-limiting toxicities (DLT) and treatment-emergent adverse events (TEAE) requiring study drug discontinuation. Assessments for DLT and TEAE will occur during Cycle 1 for Cohort A1, and during the protocol defined DLT periods for Cohort B1 and Cohort C1 (see Sections 0 and 3.3.4). TEAE will be assessed throughout the course of the trial. The primary endpoint will be the rate of DLT and TEAE requiring study drug discontinuation in the respective DLT evaluation periods of Cohort A1, Cohort B1, and Cohort C1.
- MTD or initial RP2D as monotherapy, as well as in combination with either acalabrutinib or venetoclax and rituximab.

2.5. Secondary Endpoints

Secondary endpoints in this study are related to clinical activity. These include the following:

[figure not shown]
- Objective response rate (ORR), with overall response defined as best response of complete response (CR), CR with incomplete marrow recovery (CRi), partial response (PR), or PR with lymphocytosis (PRwL) according to the 2008 International Workshop on Chronic Lymphocytic Leukemia Response Criteria (IWCLL) with modifications for treatment-related lymphocytosis.
- Duration of response (DoR), defined as time from first documentation of response to first documentation of progressive disease (PD) per 2008 IWCLL, first new therapy including allogeneic transplantation, or death due to any cause.
- Progression free survival (PFS), defined as time from first dose of study treatment to the first documentation of PD, first new therapy excluding allogeneic transplantation, or death due to any cause.
- Overall survival (OS), defined as time from first dose of study treatment to death due to any cause.
- Disease control rate (DCR) defined as the percentage of patients who have achieved CR, CRi, PR, PRwL and stable disease (SD). Duration of stable disease with stable disease defined as at least 6 months from the start of MS-553 monotherapy to first

documentation of progressive disease (PD) in relapsed and refractory CLL/SLL patients.

• Pharmacokinetics of MS-553 monotherapy, as well as the small molecule agents used in combination, acalabrutinib, or venetoclax.

[figure not shown]

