• Objective response rate (ORR), with overall response defined as best response of complete response (CR), CR with incomplete marrow recovery (CRi), partial response

(PR), or PR with lymphocytosis (PRwL) according to the 2008 International Workshop on Chronic Lymphocytic Leukemia (IWCLL) Response Criteria, with modifications for treatment-related lymphocytosis.

- Duration of response (DoR), defined as time from first documentation of response to first documentation of progressive disease (PD) per 2008 IWCLL, first new therapy including allogeneic transplantation, or death due to any cause.
- Progression free survival (PFS), defined as time from first dose of study treatment to the first documentation of PD, first new therapy (excluding allogeneic transplantation), or death due to any cause.
- Overall survival (OS), defined as time from first dose of study treatment to death due to any cause.
- Disease control rate (DCR) defined as the percentage of patients who have achieved CR, Cri, PR, PRwL and stable disease (SD). Duration of stable disease, with stable disease defined as at least 6 months from the start of MS-553 monotherapy to first documentation of progressive disease (PD) in relapsed and refractory CLL/SLL patients.
- Pharmacokinetics of MS-553 monotherapy, as well as the small molecule agents used in combination, acalabrutinib, or venetoclax.

Overview of Exploratory Endpoints

• Serum plasma, blood, and tissue biomarker assays will be used to assess:

Study Design and Methodology:

This is a Phase I/II, multi-center, open-label study of single agent MS-553, as well as MS-553 in combination with acalabrutinib or venetoclax and rituximab in treatment experienced CLL or SLL patients.

The study will consist of 3 cohorts. Cohort A will evaluate MS-553 monotherapy, Cohort B will evaluate MS-553 in combination with acalabrutinib and Cohort C will evaluate MS-553 in combination with venetoclax and rituximab.

Cohort A

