Secondary efficacy endpoints in all cohorts include overall response rate (ORR), duration of response (DoR), disease control rate (DCR), PFS, and OS. For patients achieving a response, the response duration will be measured from the time at which criteria for CR, PR, or PR with lymphocytosis is first assessed until the date at which recurrent or progressive disease or death due to disease is documented. Stable disease, a component of DCR, is defined as at least 6 months from the start of MS-553 monotherapy until to first documentation of progressive disease (PD) in relapsed and refractory CLL/SLL patients. Progression free survival will be measured as the time from the first dose of the study drug until disease progression or death from any cause. Overall survival will be measured as the time from the study drug until death due to any cause. For the secondary efficacy endpoints of response duration, PFS, and OS, patients who have not progressed or died at the time of last known status will be censored at that time; for response duration and PFS, patients may also be censored at the time

of subsequent treatment if a prior progression is not documented. See Section 8, Statistics, for more complete details on censoring.

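### PFS and duration of response are each defined in two incompatible ways, and the censoring rules that Section 6.2.2 promises in Section 8 are not there

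*Combined protocol and SAP*

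**What the plan says.** **Synopsis and Section 2.5.** These agree. PFS runs from first dose to "first documentation of PD, first new therapy excluding allogeneic transplantation, or death due to any cause" (Section 2.5; the synopsis differs only in punctuation). DoR runs from first documented response to progression, "first new therapy including allogeneic transplantation, or death due to any cause". Responses are CR, CRi, PR and PRwL.

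**Section 6.2.2.** The same endpoints are defined again:
- PFS: "Progression free survival will be measured as the time from the first dose of the study drug until disease progression or death from any cause".
- DoR start: "response duration will be measured from the time at which criteria for CR, PR, or PR with lymphocytosis is first assessed". CRi is not listed.
- DoR end: "until the date at which recurrent or progressive disease or death due to disease is documented".
- Basic censoring, for DoR, PFS and OS: "patients who have not progressed or died at the time of last known status will be censored at that time".
- New therapy: "for response duration and PFS, patients may also be censored at the time" of subsequent treatment, provided no earlier progression is documented.

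The paragraph closes by referring to Section 8 for more detail on censoring.

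**Section 8.** Section 8.8 deals only with ORR (exact 95% CI, and who leaves the denominator). Section 8.7 lists generic summaries for continuous and categorical variables. Neither mentions censoring, PFS, DoR, OS or a time-to-event method. The text of 8.8 reads as complete; the visible break is in 8.9, on exploratory analyses.

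**The concern.** An event and a censoring at the same date are mutually exclusive, so Section 6.2.2 cannot be read as a shorter version of Section 2.5. A patient who starts another non-transplant therapy without documented progression has a PFS event under 2.5. Under 6.2.2 the same patient is censored at that date if the option is used and, if it is not, is neither an event nor censored there. Two analysts could each follow the protocol and report different PFS and DoR from the same data. The study is open-label with investigator-assessed response, so an optional rule can be settled after outcomes are known.

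The situation is foreseen. Section 3.6 and the follow-up text in the synopsis and Section 3.2 list other therapy separately from progression as a reason to leave treatment. Section 4.1 admits patients who need disease reduction before allogeneic transplant.

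**Working it through.** **1. The rules side by side**

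| Situation | Synopsis and 2.5 | 6.2.2 |
|---|---|---|
| PFS, new non-transplant therapy, no PD | Event | Not an event; censoring optional |
| PFS, allogeneic transplant, no PD | Not an event; handling not stated | Not an event; censoring optional |
| DoR, any new therapy including transplant, no PD | Event | Not an event; censoring optional |
| DoR, death from another cause | Event | Not in the event list, yet the censoring sentence covers only patients who have not died |
| DoR start at CRi | Yes | Not listed (possibly shorthand for CR) |

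**2. If the optional censoring is not used.** Under Section 3.7, response data collection stops at the start of other anticancer therapy. Follow-up is then for survival (Section 3.2), with chart review and/or a phone call as the minimum (Appendix 1A, footnote b). The result depends on what *last known status* means, which is not defined: last progression assessment, or last contact alive. No figure is given for this case for that reason.

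**3. Size of the event-versus-censor difference.** The plan states no median, event count or power for PFS or DoR, so there is no figure of its own to reproduce. Assumptions, none from the documents: constant hazards, censoring independent of outcome, and a 12-month median to progression or death. Let s be the share of first exits that are new therapy without progression.

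- Hazard of progression or death: λ = ln 2 / 12.
- Hazard of new therapy: h = λs / (1 − s).
- Median with new therapy as an event: ln 2 / (λ + h) = 12(1 − s).
- Median with new therapy censored: ln 2 / λ = 12.0.
- Ratio, censored to event: 1 / (1 − s), whatever the underlying median.

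| s | Event (2.5) | Censored (6.2.2) | Censored median longer by |
|---|---|---|---|
| 10% | 10.8 months | 12.0 months | 11% |
| 20% | 9.6 months | 12.0 months | 25% |
| 30% | 8.4 months | 12.0 months | 43% |

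A simulation of 400,000 patients per value of s gave the same medians. The same ratios hold for DoR if s is the share of responses that end first by new therapy, transplant included.

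**4. Direction.** On the same data, censoring at new therapy instead of counting it as an event can only leave the Kaplan-Meier curve unchanged or raise it. Omitting CRi works the other way: it can delay the start of DoR and shorten it.

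**5. Compared with sampling error.** The 95% CI of an exponential median with d = n(1 − s) events, relative to the estimate, runs from 2d/χ²(0.975; 2d) − 1 to 2d/χ²(0.025; 2d) − 1. At s = 30%:

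| Group | n | d | 95% CI |
|---|---|---|---|
| B3 | 10 | 7 | −46% to +149% |
| B2 or C2 | 20 | 14 | −37% to +83% |
| A2, first 25 | 25 | 17.5 | −34% to +70% |
| A2 pooled with the 40 added | 65 | 45.5 | −24% to +37% |

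The move from 12.0 to 8.4 months is −30%. It lies inside the interval for 10 to 25 patients and outside it only for pooled A2. At s = 20% the pooled interval (d = 52) starts at −22%, so a −20% move is inside; at s = 10% it starts at −21%, so −10% is inside.

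**The case against.** The wording conflict itself is hard to dispute. The case against its importance has four parts.

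- **Reach.** Section 5.2.5 bars other anticancer therapy before progression, and the one such therapy that eligibility anticipates is allogeneic transplant, which Section 2.5 does not count as a PFS event. For PFS the direct clash is therefore confined to non-transplant therapy before progression, for example after stopping for toxicity. This stands and narrows the PFS side. It does not help DoR, where 2.5 counts transplant as an event, and 2.5 still leaves transplant unhandled for PFS.
- **Size.** The shares and the 12-month median are assumptions. Even at 30% the shift exceeds sampling error only in pooled A2, a group that mixes dosing regimens and is assumed to be followed to an exit in full. This stands as a limit on materiality. But both rules are applied to the same patients, so the gap is a fixed difference in one direction, and wide intervals do not remove it.
- **Minor items.** CRi may be shorthand, and the censoring sentence leans towards counting any death in DoR. Both are fair; they are drafting points secondary to the main conflict.
- **Consequence.** There is no hypothesis test (Section 8.4), and the primary safety endpoints do not use these definitions. This is correct, and it keeps the point below the most serious level.

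A separate analysis plan might hold the missing rules, but Section 6.2.2 refers to Section 8 of this document.

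**Conclusion.** The concern holds: the plan is wrong as written and should be fixed. PFS and DoR each have two definitions that cannot both be applied, the treatment of new therapy is left optional, and the reference to censoring rules in Section 8 leads to nothing. Confidence in the textual conflict is high.

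The size in practice is unknown, because it depends on how many patients start new therapy without progression. On the assumed inputs above, the censored median is 11% to 43% longer than the event-based one for shares of 10% to 30%. The effect is confined to descriptive secondary estimates.

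**What to change.** In Section 6.2.2, adopt the definitions that the synopsis and Section 2.5 already share:
- DoR starts at first CR, CRi, PR or PRwL.
- Death from any cause is an event for both endpoints.
- First new therapy is an event for both, excluding allogeneic transplant for PFS and including it for DoR. This replaces the optional censoring.
- *Last known status*, for PFS and DoR, is the last adequate response assessment.
- The sponsor states one analysis rule for PFS after allogeneic transplant: censor at it or follow through it.

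In Section 8.8, set out these event and censoring rules and specify Kaplan-Meier medians with 95% CIs for PFS, DoR (responders) and OS. A sensitivity analysis that censors at new therapy is optional.

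The cost is wording in two sections, plus a check that the start date of subsequent therapy is collected in follow-up. Section 6.1.8 requires medications given during the study to be recorded and Section 5.3 puts withdrawal reasons on the CRF, so it may already be captured; the eCRF content is not in the documents. No treatment or visit changes.
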